2.7.3 Handling of missing values/censoring/discontinuations

For the analysis of secondary endpoints, if a patient has no post-baseline value at the given time point (Week 4 or Week 12), the missing value will not be imputed and the patient will be removed from the analysis.

2.8 Safety analyses

All safety analyses will be based on the SS unless otherwise specified. There will be no inferential analyses of the safety data.

2.8.1 Adverse events

2.8.1.1 Coding of AEs

Adverse events (AEs) will be coded using MedDRA terminology (v21.1 or later).

2.8.1.2 General rules for AE reporting

AE summaries will include all treatment-emergent AEs (TEAEs). TEAEs are defined as AEs starting on or after the first day of study treatment. All AEs will be listed. AEs starting prior to the first day of study treatment (non-TEAEs) will be flagged in the listings.

All TEAEs will be summarized by study phase as defined in Section 2.1.1.

TEAEs will be summarized by presenting the number and percentage of patients having at least one TEAE, having at least one TEAE in each primary SOC, and for each PT using MedDRA terminology. A patient with multiple occurrences of a TEAE will be counted only once in the AE category.

Separate summaries will be presented by SOC, PT and severity. A patient with multiple severities for an AE will be summarized under the worse severity recorded for the event.

Any information collected will be listed as appropriate.

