## **7.2 Serious adverse events**

### **7.2.1 Definition of SAE**

An SAE is defined as any adverse event [appearance of (or worsening of any pre-existing)] undesirable sign(s), symptom(s) or medical condition(s) which meets any one of the following criteria:

- is fatal or life-threatening
- results in persistent or significant disability/incapacity
- constitutes a congenital anomaly/birth defect
- requires inpatient hospitalization or prolongation of existing hospitalization, unless hospitalization is for:
  - routine treatment or monitoring of the studied indication, not associated with any deterioration in condition (specify what this includes)
  - elective or pre-planned treatment for a pre-existing condition that is unrelated to the indication under study and has not worsened since signing the informed consent
  - treatment on an emergency outpatient basis for an event not fulfilling any of the definitions of a SAE given above and not resulting in hospital admission
  - social reasons and respite care in the absence of any deterioration in the patient's general condition
  - is medically significant, e.g. defined as an event that jeopardizes the patient or may require medical or surgical intervention.

All malignant neoplasms will be assessed as serious under "medically significant" if other seriousness criteria are not met.

Life-threatening in the context of a SAE refers to a reaction in which the patient was at risk of death at the time of the reaction; it does not refer to a reaction that hypothetically might have caused death if it were more severe (see Annex IV, ICH-E2D Guideline).

Medical and scientific judgment should be exercised in deciding whether other situations should be considered serious reactions, such as important medical events that might not be immediately life threatening or result in death or hospitalization but might jeopardize the patient or might require intervention to prevent one of the other outcomes listed above. Examples of such events are intensive treatment in an emergency room or at home for allergic bronchospasm, blood dyscrasias or convulsions that do not result in hospitalization or development of dependency or abuse (see Annex IV, ICH-E2D Guideline).

Any suspected transmission via a medicinal product of an infectious agent is also considered a serious adverse reaction.

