### **9.5.2 Safety variables**

The safety and tolerability assessments are listed below:

- AEs and SAEs
- Sitting systolic, diastolic BP, and pulse pressure
- Heart rate
- Laboratory values

The assessment of safety will be based primarily on the frequency of adverse events, SAEs, and laboratory abnormalities. Other safety data will be summarized as appropriate.

The incidence of treatment-emergent adverse events (new or worsened) will be summarized by primary system organ class, preferred term, severity, and relationship to study drug. In addition, the incidence of death, SAEs, and AEs leading to discontinuation will be summarized separately by primary system organ class and preferred term.

Laboratory data will be summarized by presenting shift tables using extended reference ranges (baseline to most extreme post-baseline value), by presenting summary statistics of raw data and change from baseline values (mean, median, standard deviation, 25th and 75th percentiles, interquartile range, minimum and maximum) and by the flagging of notable values in data listings.

[figure not shown]

[figure not shown]
Data from other tests (e.g., vital signs) will be listed, notable values will be flagged, and any other information collected will be listed as appropriate.

Safety analyses will be performed based on the Safety Set. There will be no inferential analyses of the safety data. See [Section 9.5.1](#).

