2.8.1.3 AE summaries

The following summary tables will be provided:

- AEs, regardless of study treatment relationship, by primary SOC, PT and worst severity
- Most frequent ($\geq 5\%$) AEs, regardless of study treatment relationship, by PT
- Most frequent ($\geq 5\%$) non-serious AEs, regardless of study treatment relationship, by PT
- AEs, suspected to be related to study treatment, by primary SOC and PT
- Serious adverse events (SAEs), regardless of study treatment relationship, by primary SOC and PT
- SAEs, suspected to be related to study treatment, by primary SOC and PT
- SAEs occurring with a frequency of $\geq 0.5\%$, regardless of study treatment relationship, by PT
- SAEs, regardless of study treatment relationship, by primary SOC, PT and seriousness criteria
- AEs leading to discontinuation, regardless of study treatment relationship, by primary SOC and PT

- AEs requiring dose adjustment or study treatment interruption, regardless of study treatment relationship, by primary SOC and PT
- AEs requiring additional therapy, regardless of study treatment relationship, by primary SOC and PT
- Death resulting from AEs, regardless of study treatment relationship, by primary SOC and PT

In addition, an overview of TEAEs presenting the number and percentage of patients having at least one TEAE for each of the above categories will be provided.

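### The SAP defines treatment-emergent AEs by start date alone, where the protocol also counts worsened events, and does not declare the change

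*SAP*

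**What the plan says.** Protocol 9.5.2 states the planned safety summary: "The incidence of treatment-emergent adverse events (new or worsened) will be summarized by primary system organ class, preferred term, severity", and also by relationship to study drug. It adds that "the incidence of death, SAEs, and AEs leading to discontinuation will be summarized separately by primary system organ class and preferred term", with no limit on when those events began.

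SAP 2.8.1.2 says "AE summaries will include all treatment-emergent AEs (TEAEs") and then fixes the term: "TEAEs are defined as AEs starting on or after the first day of study treatment". Events with earlier onset are dealt with in one sentence: "AEs starting prior to the first day of study treatment (non-TEAEs) will be flagged in the listings". SAP 2.8.1.3 lists the AE tables and closes with "an overview of TEAEs presenting the number and percentage of patients having at least one TEAE for each of the above categories".

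SAP section 4 lists the changes to protocol-specified analyses, down to the removal of CPK from the notable laboratory values. The change in the treatment-emergent definition is not on the list.

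**The concern.** The two documents give different rules for the same tables. Under the protocol, an event already open at first dose counts if it worsens on treatment. Under the SAP it does not, whatever happens to it later.

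Protocol 9.5.2 bases the safety assessment mainly on the frequency of AEs, SAEs and laboratory abnormalities. The AE tables are where on-drug deterioration should show. If a screening-onset event becomes serious on study drug, or leads to a dose change or to stopping treatment, a reader of the AE, SAE, discontinuation or dose-adjustment table would not see it and would have no notice that the rule had been narrowed.

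**Working it through.** The documents state no figure to reproduce here, so the check is a comparison of texts.

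**1. Which events the two rules treat differently.** The protocol counts an event that is new on treatment or that worsens on treatment. The SAP counts an event only if its start date is on or after the first day of treatment. They differ for events that start before first dose and worsen on or after it. AEs are collected from consent (protocol 7.1), and screening lasts up to 6 weeks, 6 × 7 = 42 days (protocol 3.1 and Table 6-1). The affected onset window is therefore consent to first dose, 42 days at most. It is often likely to be shorter, because protocol 3.1 lets patients be randomized once screening criteria are met.

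**2. Which events are not affected.** Conditions present before consent are recorded as medical history (protocol 6.2 and 6.5.2). If one worsens on study drug, the worsening is an AE with an on-drug start date, and the SAP rule counts it. Under SAP 5.1.2, an AE with a missing start day in the month of first dose is given the first-dose date, so it is counted too.

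**3. Whether a worsened event keeps its start date.** Three provisions suggest that it does:
- Protocol 7.1 has a detected AE followed to its end, with changes in severity assessed at each visit, so it is handled as one event.
- Protocol 7.2.2 has progression of an SAE reported as follow-up to the original event.
- SAP 2.8.1.2 expects one AE to carry several severities and counts the worst.

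One provision could point the other way. The SAE definition in protocol 7.2.1 covers "appearance of (or worsening of any pre-existing)] undesirable sign(s), symptom(s) or medical condition(s"), so some sites might open a new record when an event becomes serious. No section says whether a worsened non-serious AE gets a new eCRF record.

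**4. Which outputs lose the event.** SAP 2.8.1.2 governs the AE summaries. The tables in 2.8.1.3 include SAEs, AEs leading to discontinuation, and AEs requiring dose adjustment or interruption. The instruction to include all TEAEs does not literally say only TEAEs. But the overview counts TEAEs for each of these categories, and the only output named for non-TEAEs is the listings.

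**5. Which outputs still capture part of it.**
- SAP 2.8.2 summarizes deaths on the FAS without a TEAE filter.
- SAP 2.8.3 gives the incidence of hyperkalemia and of worsening renal function through Week 12 from central laboratory data.
- SAP 2.8.4.1 gives the incidence of systolic pressure below 90 mmHg through Week 12 from vital signs.
- SAP 2.8.4.2 tabulates HF signs and symptoms by visit.
- SAP 2.3.1 counts adverse event as a reason for stopping study treatment, but not by preferred term.

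**6. Size.** The documents do not say how many patients reach first dose with an open AE, or how many of those AEs worsen, so no count can be derived. The sensitivity of the frequency tables can be shown. Assume 216 treated per arm and cut-offs applied per arm (the SAP does not say whether they are):
- SAE table at ≥0.5%: 1/216 = 0.46% falls below and 2/216 = 0.93% meets it.
- AE table at ≥5%: 10/216 = 4.63% falls below and 11/216 = 5.09% meets it.

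A preferred term that sits just at a cut-off can leave either table through one omitted patient.

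**The case against.** The strongest reply is that little is lost. The named main risks (hypotension, renal dysfunction, hyperkalemia) are the best covered outside the AE tables, as step 5 shows. Eligibility limits the examples: potassium above 5.2 mEq/L or eGFR below 30 ml/min/1.73 m² at screening excludes a patient, and the blood pressure criterion applies at both screening and pre-randomization. Events open at first dose precede treatment, so they should be balanced between arms in expectation, and SAP 2.8 plans no inferential safety analysis. The loss also depends on a recording convention that is not written down.

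Most of this stands, and it limits the point. It does not remove it. Laboratory and vital-sign incidences do not replace the SAE, discontinuation and dose-adjustment tables. Balance at first dose does not carry over to worsening afterwards, which can depend on the drug. A missing convention is a further reason for the SAP to settle the matter.

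A reader might infer three stronger things that the documents do not support:
- That such events vanish from every safety output except a listing. Deaths and the items in step 5 are still summarized.
- That the gap is wide because these problems are common in heart failure before enrolment. Conditions present before consent are medical history, and their worsening is counted.
- That a number of lost patients can be given. Any count would rest on two assumed rates for which the documents offer no basis.

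**Conclusion.** The point holds in limited form. The SAP rule is narrower than protocol 9.5.2, and section 4 does not declare the narrowing. The tables affected are those in SAP 2.8.1.3. The events affected are AEs with onset between consent and first dose that worsen or become serious on study drug and keep their original start date. Retention of the start date is well supported for progression of an existing SAE (protocol 7.2.2), is suggested by protocol 7.1 for other AEs, and is confirmed nowhere for non-serious AEs. The number of patients cannot be estimated and is probably small, since an event must begin in a window of at most 42 days, still be open at first dose, and then worsen. The primary endpoint is not touched. The case for correction is that an undeclared departure in the main safety tables can be repaired cheaply before lock.

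**What to change.** Change the definition in SAP 2.8.1.2 to: TEAE = AE starting on or after first dose, or starting before first dose and increasing in severity or becoming serious on or after first dose. Assign study phase for the second group by the date of worsening. State where the worsening and its date are recorded. Keep this consistent with protocol 7.2.2: progression of an existing SAE stays as follow-up to the original event and should not have to be entered as a new one.

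If the sponsor prefers the start-date rule, it should be listed in SAP section 4 with a reason. That makes the departure visible but does not restore the protocol's analysis.

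The cost is one sentence on the definition, a short statement on recording, a derivation change, possibly a few data queries where no worsening date was captured, and slightly higher AE counts. The documents do not show whether the eCRF holds a worsening date, so the query load should be checked first. SAP Amendment 1 is dated before database lock, so the change can be made while the data are still open to queries.

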2.8.1.3 AE summaries

The following summary tables will be provided:

- AEs, regardless of study treatment relationship, by primary SOC, PT and worst severity
- Most frequent ($\geq 5\%$) AEs, regardless of study treatment relationship, by PT
- Most frequent ($\geq 5\%$) non-serious AEs, regardless of study treatment relationship, by PT
- AEs, suspected to be related to study treatment, by primary SOC and PT
- Serious adverse events (SAEs), regardless of study treatment relationship, by primary SOC and PT
- SAEs, suspected to be related to study treatment, by primary SOC and PT
- SAEs occurring with a frequency of $\geq 0.5\%$, regardless of study treatment relationship, by PT
- SAEs, regardless of study treatment relationship, by primary SOC, PT and seriousness criteria
- AEs leading to discontinuation, regardless of study treatment relationship, by primary SOC and PT

- AEs requiring dose adjustment or study treatment interruption, regardless of study treatment relationship, by primary SOC and PT
- AEs requiring additional therapy, regardless of study treatment relationship, by primary SOC and PT
- Death resulting from AEs, regardless of study treatment relationship, by primary SOC and PT

In addition, an overview of TEAEs presenting the number and percentage of patients having at least one TEAE for each of the above categories will be provided.

2.8.1.4 Adverse events of special interest / grouping of AEs

Separate summaries will be provided for AEs related to all angioedema and positively adjudicated angioedema, regardless of study treatment relationship. The summaries will be presented by primary SOC, PT and worst severity.

2.8.2 Deaths

Patient deaths will be summarized by primary SOC, PT and study phase (see Section 2.1.1 for study phase definitions), and whether an autopsy was performed. A patient listing of all deaths with primary and contributing reasons for death will be provided. All patients in FAS will be included for the above analysis. Deaths will be coded using MedDRA terminology (v21.1 or later).

2.8.3 Laboratory data

Laboratory values will be summarized using shift tables (from baseline to most extreme post baseline value) by each laboratory parameter at its worst severity by study phase (see Section 2.1.1 for study phase phase definitions). The number and percentage of patients with laboratory values will be presented by low/normal/high (low and high) classifications to compare baseline to worst post baseline value. Unscheduled assessments will be considered.

In addition, laboratory values and the change from baseline for each parameter by visit will be summarized by treatment group and open-label sacubitril/valsartan. In the event there are multiple laboratory values within a visit, the worst value will be summarized.

A separate summary table will be presented by study phase (see Section 2.2.1 for study phase phase definitions) with the number and percentage of patients having notable lab abnormalities based on percent change from baseline (see Section 5.3 for a list of notable laboratory abnormalities). Unscheduled assessments will be considered.

Listings of all laboratory values will be provided. A separate listing for pregnancy tests will also be provided. Any notable laboratory abnormalities will be flagged.

Laboratory values indicated as $<x$ will be converted to $(0.5)(x)$ for purposes of analysis. Laboratory values indicated as $>x$ will be converted to the values specified in the below table for purposes of analysis.

Laboratory Test	Unconverted Value	Converted Value for Analysis
Red Blood Cell Count	>7.00	7.1
Potassium	>7.0	7.1
Urine Erythrocytes	>182	182.1
Urine Leukocytes	>182	182.1

The incidence of hyperkalemia through Week 12 will be calculated by treatment group. The relative risk (sacubitril/valsartan vs. enalapril) and 95% confidence interval will be presented. Hyperkalemia will be determined from the central laboratory data as potassium >5.3 mEq/L. Unscheduled assessments will be considered.

Similarly, the incidence of worsening renal function through Week 12, relative risk (sacubitril/valsartan vs. enalapril) and 95% confidence interval will be presented. Worsening renal function will be determined from the central laboratory data as a worsening (decrease) in eGFR of $\geq 35\%$ from baseline, or an increase in creatinine of ≥ 0.5 mg/dL from baseline and a worsening (decrease) in eGFR of $\geq 25\%$ from baseline. Unscheduled assessments will be considered.

2.8.4 Other safety data

2.8.4.1 Vital signs

All vital signs (systolic and diastolic blood pressure [mmHg], pulse rate [beats per minute], respiration rate [breaths per minute], weight [kg], height [cm], and BMI [kg/m²]) will be descriptively summarized at each visit by treatment group and open-label sacubitril/valsartan. Change from baseline will also be presented.

A separate summary table will be presented with the number and percentage of patients having notable vital signs based on changes relative to baseline values (see Section 5.4 for a list of notable vital signs) by study phase (see Section 2.1.1 for study phase definitions). Unscheduled assessments will be considered.

The incidence of hypotension through Week 12 will be calculated by treatment group. The relative risk (sacubitril/valsartan vs. enalapril) and 95% confidence interval will be presented. Hypotension will be determined from the vital signs data as systolic blood pressure <90 mmHg. Unscheduled assessments will be considered.

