#### **3.6.1 Risks**

Experience in the PARADIGM-HF trial, both in the run-in period as well as the double-blind randomization period, indicated that the major risks associated with the treatment of sacubitril/valsartan are renal dysfunction, [426 (10.14%) in 4203 patients in the double-blind treatment period], hyperkalemia, [488 (11.61%) in 4203 patients in the double-blind treatment period], and hypotension [740 (17.61%) in 4203 patients in the double-blind treatment period].

In PARADIGM-HF, patients treated with enalapril experienced these events at a similar rate with the exception of hypotension; renal dysfunction, [487 (11.52%) in 4229 patients in the double-blind treatment period]; hyperkalemia, [592 (14%) in 4229 patients in the double-blind treatment period]; and hypotension, [506 (11.97%) in 4229 patients in the double-blind treatment period]. Results from the TITRATION study indicated that patients whom are ACE or ARB naïve are at an increased risk of experiencing these adverse events.

In this study, the risk of experiencing renal dysfunction, hyperkalemia, and hypotension are mitigated by appropriate up-titration of the drug every two weeks. The risks are further mitigated by appropriate inclusion and exclusion criteria. Patients entering into the study must have an SBP of at least 140 mmHg if not treated for hypertension or a SBP of >105 mmHg if

they are currently on treatment. Additionally, patients are excluded if they have an eGFR < 30 ml/min/1.73 m^2 or a potassium > 5.2 mEq/L at screening.

Drug to drug interactions are known to occur with concomitant use of ACE/ARB/NEP and renin inhibitors. See [Section 5.5.8](#) for prohibited medications. Patient will be provided with study treatment instructions and their medication histories will be reviewed at Screening and all subsequent visits.

Sacubitril/valsartan, [19 (0.5%) in 4203 patients in the double-blind treatment period of PARADIGM-HF] and enalapril 10 (0.2%) in 4229 patients in the double-blind treatment period of PARADIGM-HF] may also cause angioedema. The risk of developing angioedema is increased if patients take both an ACEi and sacubitril/valsartan. To decrease this risk, patients will be required to undergo a 36-hour washout prior to randomization as well as the open-label treatment epoch to minimize the interaction between an ACEi and sacubitril/valsartan in potentiating the development of angioedema.

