### **5.5.4 Instructions for prescribing and taking study treatment**

Novartis will supply the investigators with all medications sufficient for the course of the study. Patients will be provided with medication packs containing study drug corresponding to their assigned treatment arm and dose level, sufficient to last until the next scheduled visit. Patients will be instructed to hold their morning study medication dose on the day of study visits. Study drug will be administered at the site after pre-dose vital signs, blood samples and assessments are performed. Vital signs will include blood pressure, pulse and respiration measurements. BP will be measured using a standard sphygmomanometer with an appropriate sized cuff and the non-dominant arm in the seated position after 5 minutes of rest, with back supported and both feet placed flat on the floor. Every effort should be made to use the same arm for the patient for all vital signs assessments and where possible, the same person doing the assessment.

In order to adequately blind the study, patients will be required to take their assigned active treatment tablet along with placebo matching the opposite treatment twice daily. Patients will be instructed to take a total of two tablets by mouth twice a day for the duration of the double-blind treatment epoch, as follows:

- one tablet from the sacubitril/valsartan/sacubitril/valsartan matching placebo pack, and;
- one tablet from the enalapril/enalapril matching placebo pack

Table 5-5 summarizes the study drug that will be taken during the double-blind treatment epoch by visit and Table 5-6 summarizes the study drug that will be taken during the open-label treatment epoch.

Forced-titration will proceed according to the following table:

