#### 6.4.1 Hemodynamic Assessments using arterial tonometry

Hemodynamic assessment of arterial parameters during trough and 4 hours post-dose will be obtained using the methods, custom instrumentation and software reported by (Mitchell, et al. 2008, 2010, and 2011). Auscultatory brachial blood pressure will be assessed by using the computer-controlled NIHem device, which is capable of digitizing the cuff pressure, electrocardiogram (1000 Hz) and a cuff microphone channel (12 kHz) throughout the inflation and deflation sequence in order to allow for over-read of all blood pressure acquisitions by the Hemodynamic Core Lab. A detailed manual with instructions on performing hemodynamic assessments using arterial tonometry will be provided to all sites.

Hemodynamic trough assessments will be performed at approximately 08:00 hrs., prior to administration of study drug. A time window between 07:00 and 11:00 hrs. is permitted to accommodate patient schedules while still allowing for the 4-hr post-dose assessment to be completed the same day. The Screening/Baseline assessment will be obtained between day -7 to day -2 window to allow for a repeat test for quality assurance, if necessary, prior to Randomization on Day 1 (Visit 2).

During treatment with study medication, hemodynamic trough and 4-hr., post-dose assessments will be performed at Weeks 4, 12 and 24 (Visits, 5, 6 and 8). The patient will be provided with the following instructions:

- Take study medication the evening before the actual visit and no less than 12 hrs. prior to the scheduled assessment time.
- No cigarettes or caffeinated beverages within 6 hrs. before (or between) studies.
- Remain NPO after 12MN until after the 08:00 hemodynamic trough.

**Note:** Patients may eat a light snack or breakfast after the 08:00 hemodynamic trough assessment. This would include a low glycemic energy bar or something that most people, including diabetic, would be able to tolerate. The meal time will be recorded in the source document.

- Patients will then remain in or near the clinic until the hemodynamic assessment at 4-hrs post-dose ( $\pm 0.5$  hrs.) is performed at 12:00.
- Dress in comfortable clothing, preferably shorts, to allow access to anatomical pulse recording sites. A patient gown may also be provided.
- Arrive at the clinic one-half hour before the hemodynamic assessment, which will take approximately 1 hour.
- Rest in a comfortably supported supine posture for 15–20 minutes.

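### The hypotension incidence through Week 12 rests on seated, pre-dose scheduled readings, and the 4-hour post-dose cuff pressures at Weeks 4 and 12 do not enter it

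*SAP*

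**What the plan says.** SAP 2.8.4.1 sets the measure: "The incidence of hypotension through Week 12 will be calculated by treatment group". It names one data source: "Hypotension will be determined from the vital signs data as systolic blood pressure <90 mmHg". It adds an effect measure, "The relative risk (sacubitril/valsartan vs. enalapril) and 95% confidence interval will be presented", and one widening of the source, "Unscheduled assessments will be considered".

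Protocol 5.5.4 fixes when scheduled vital signs are taken relative to dose: "Patients will be instructed to hold their morning study medication dose on the day of study visits", and "Study drug will be administered at the site after pre-dose vital signs, blood samples and assessments are performed". Footnote 16 to Table 6-1 agrees. The sequence in Protocol 6.5.1 puts vital signs ahead of the hemodynamic assessments, and Table 6-1 has no post-dose vital-signs row. Protocol 6.5.4 has the reading taken sitting.

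Protocol 6.4.1 describes a second blood pressure measurement: "Auscultatory brachial blood pressure will be assessed by using the computer-controlled NIHem device". This cuff pressure is digitized and over-read by the core laboratory. It belongs to hemodynamic assessments done at trough and 4 hours post-dose at Weeks 4, 12 and 24, after supine rest. The visible hypotension rule does not mention it.

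**The concern.** Protocol 3.6.1 names three major risks of sacubitril/valsartan: renal dysfunction, hyperkalemia and hypotension. Comparing the arms of the earlier outcome trial, it says "patients treated with enalapril experienced these events at a similar rate with the exception of hypotension". Hypotension is therefore the tolerability contrast that readers will look for.

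A table titled as an incidence through Week 12 would not tell them that every scheduled reading behind it was taken before the morning dose. A patient whose systolic pressure drops below 90 mmHg after dosing and recovers by the next visit is not counted, unless an unscheduled reading happens to catch it. The trial already records pressure 4 hours after dosing at two visits inside the window, so this gap could be examined without any new procedure.

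**Working it through.** **1. Which readings count.** Inputs are Protocol Tables 5-5 and 6-1, Protocol 5.5.4 and 6.4.1, and SAP 2.8.4.1. The dose level shown is the one taken up to the visit under planned titration.

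| Visit | Dose level before visit | Seated vital signs (counted) | Supine NIHem trough (not counted) | Supine NIHem 4 h post-dose (not counted) |
|---|---|---|---|---|
| Week 1 | 1 | pre-dose | none | none |
| Week 2 | 1 | pre-dose | none | none |
| Week 4 | 2 | pre-dose | yes | yes |
| Week 12 | 3 | pre-dose | yes | yes |

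Scheduled readings counted: 4, all pre-dose, of which 1 (Week 12) follows the step to Dose Level 3. Scheduled post-dose cuff readings in the same window: 2, neither counted.

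**2. The plan's own background figures.** The documents state no expected hypotension incidence for this trial. The rates cited in Protocol 3.6.1 reproduce: 740/4203 = 17.61% and 506/4229 = 11.97%. The ratio is 1.47 and the difference 5.6 points. They are reported rates over the double-blind period of another trial and are not said to be measured systolic pressure below 90 mmHg. They serve below only as a scale.

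**3. Illustration A: the same share of events is captured in both arms (assumption).** Take risks p1 = 0.1761 and p0 = 0.1197, n = 216 per arm (Protocol 9.8), and capture share s. Then RR = (s·p1)/(s·p0) = p1/p0, which does not depend on s. The standard error of log RR is √[(1 − s·p1)/(n·s·p1) + (1 − s·p0)/(n·s·p0)].

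At s = 1: √(0.8239/38.04 + 0.8803/25.86) = √(0.02166 + 0.03405) = 0.236, so the interval is 1.47 × exp(±1.96 × 0.236) = 0.93 to 2.34.

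| Share captured | Risks | RR (95% CI) | Risk difference |
|---|---|---|---|
| 100% | 17.6% vs 12.0% | 1.47 (0.93–2.34) | 5.6 points |
| 75% | 13.2% vs 9.0% | 1.47 (0.85–2.54) | 4.2 points |
| 50% | 8.8% vs 6.0% | 1.47 (0.74–2.91) | 2.8 points |
| 25% | 4.4% vs 3.0% | 1.47 (0.55–3.92) | 1.4 points |

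Incidence and risk difference shrink and the interval widens, while the ratio stays put.

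**4. Illustration B: a shift in a normal distribution (assumption).** Risk at one reading = Φ((90 − mean)/SD), with SD 15 mmHg, enalapril trough mean 120 and sacubitril/valsartan trough mean 117. None of these values is in the documents.

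| Scenario | Means, enalapril / sacubitril/valsartan | Risks, enalapril vs sacubitril/valsartan | RR | Risk difference |
|---|---|---|---|---|
| Trough | 120 / 117 | 2.3% vs 3.6% | 1.58 | 1.3 points |
| 4 h, both arms 5 mmHg lower | 115 / 112 | 4.8% vs 7.1% | 1.49 | 2.3 points |
| 4 h, sacubitril/valsartan a further 2 mmHg lower | 115 / 110 | 4.8% vs 9.1% | 1.91 | 4.3 points |

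Both risks and the risk difference are larger at 4 hours in each case. The RR is lower than at trough in one case and higher in the other. The risk difference would not grow if the post-dose fall were sufficiently larger on enalapril: 120 − 5 − 3 = 112 equals 117 − 5 = 112, which gives a difference of zero.

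**The case against.** The strongest defence is that the SAP follows the protocol's declared safety variable. Protocol 9.5.2 lists sitting blood pressure, and Appendix 1 applies the 90 mmHg cut-off to vital signs. Both arms are read at the same point in the dosing interval, so the comparison is like for like, and choosing trough over 4 hours is a choice of what to estimate. The NIHem reading is supine and from a different device. Safety is descriptive under SAP 2.8. Hypotension is also picked up through adverse events, which are sought at every visit and can be volunteered between visits, through the dose-adjustment and discontinuation tables, and through the reasons for not reaching Dose Level 3. Redacted parts of the SAP may summarise the post-dose pressures.

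Most of this stands, and it limits the point to labelling and one additional summary. It rules out a pooled seated-or-supine incidence. It does not remove the gap: the other sources are reported events or reasons, not measured pressure below 90 mmHg, and whatever the redacted text contains, the visible hypotension rule draws on vital signs alone.

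Some stronger inferences are tempting but unsupported:

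- *The relative risk is pulled toward 1 and tolerability is made to look better than it is.* No document gives the trough-to-4-hour change by arm. Equal capture leaves the ratio unchanged, and otherwise it can rise or fall.
- *Drug effect on pressure is at its lowest when vital signs are taken.* The protocol does call the pre-dose hemodynamic study a trough, but it gives no blood pressure time course. Protocol 3.3 describes NEP inhibition as sustained over 24 hours at the target dose.
- *Every scheduled reading is at least 12 hours after the last dose.* That instruction covers the hemodynamic visits, so Weeks 4 and 12 only. For Weeks 1 and 2 it would be inferred from twice-daily dosing.
- *The Week 4 post-dose reading follows the first target-level dose.* The documents do not say which dose level the Week 4 clinic dose is.

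**Conclusion.** The point holds as a matter of labelling and unused data. All 4 scheduled on-treatment readings behind the hypotension incidence are seated and pre-dose, 1 of the 4 follows the step to Dose Level 3, and 2 scheduled post-dose cuff readings per patient fall in the same window without entering the visible rule. If pressure is lower after dosing, the absolute incidence is understated. The risk difference is understated too, unless the post-dose fall is sufficiently larger on enalapril. The size cannot be derived from the documents; the illustrations rest on assumed capture shares and assumed blood pressure distributions. No direction can be claimed for the relative risk. This is a worthwhile, inexpensive improvement to a descriptive safety summary. It does not show that the planned comparison between arms is biased.

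**What to change.** In SAP 2.8.4.1:

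1. Label the scheduled vital-signs result as seated and pre-dose, with a note that unscheduled readings are included and have no fixed timing relative to dose.
2. Add a separate summary of systolic pressure below 90 mmHg from the supine NIHem readings at 4 hours post-dose at Weeks 4 and 12: incidence by arm, relative risk and 95% confidence interval. The denominator is patients with a reading at that time point.
3. Show the NIHem trough readings from the same visits beside it, so that trough and post-dose are compared in the same posture and on the same device.
4. Do not combine seated and supine readings into one headline incidence.

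The cost is a few lines of SAP text and one extra descriptive table from data already collected, with no new visit or procedure. The downside is that the added table uses a different posture and device from the vital signs, so its figures cannot be set directly against the seated incidence.
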